## 3.0 Study design and procedures

A 10-week non-randomized, controlled, parallel-arm trial, divided into a 2-week baseline and an 8-week intervention will be implemented. Older subjects with overweight or obesity (n = 20) will be assigned to 1

*Time restricted feeding with physical activity for weight management Version 4, 07/19/21*  of 4 groups: (1) TRE (n = 5) ad libitum food intake from 12 pm to 8 pm, fasting (with zero-calorie beverages) from 8 pm to 12 pm daily, (2) TRE + EN (n = 5), TRE diet as stated in group 1 plus 3-4 days of 40-60 minutes of endurance exercise per week; or 3) TRE + RT (n = 5), TRE diet as stated in group 1 plus 3-4 days of 40-60 minutes of resistance training per week 4) control (n = 5), ad libitum food intake daily with no meal timing restrictions. In-person study activities will be carried out at the Human Nutrition Research Unit (HNRU) located in the Applied Health Sciences Building ([name]) or at Coalition Strength and Conditioning ([name]).

#### **Diet and exercise interventions**

Group	Diet protocol	Exercise protocol
TRE (n = 50)	8-h eating window Ad libitum food intake from 12-8 pm every day Fasting from 8-12 pm every day (16-h fast)	None
TRE + EN (n = 50)	8-h eating window Ad libitum food intake from 12-8 pm every day Fasting from 8-12 pm every day (16-h fast)	4 days/week, supervised 60 minutes, Intensity: 85% HRmax
TRE + RT (n = 50)	8-h eating window Ad libitum food intake from 12-8 pm every day Fasting from 8-12 pm every day (16-h fast)	4 days/week, supervised 60 minutes, Intensity: 85% RPE
Control (n = 50)	Every day: Ad libitum fed	No exercise

# Diet protocol

TRE group and combination groups (8-h eating window): During the weight loss period, the TRE groups will be instructed to eat ad libitum from 12-8pm daily, and fast from 8-12 pm (16-h fast). During the 8-h eating window, there will be no restrictions on types or quantities of foods consumed. Moreover, participants will not be required to monitor caloric intake during this ad libitum feeding period. During the fasting period, participants will be encouraged to drink plenty of water and will be permitted to consume energy-free drinks, such as black tea, coffee, and diet sodas (limit 2 diet sodas/d, since these beverages may increase sugar craving ). TRE participants will meet with the dietitian every week (by phone or zoom) throughout the weight loss period to review their diet adherence. Subjects will also be taught how to make healthy food choices that conform to ADA nutrition guidelines.

#### **Exercise protocol**

Study week	Week 1-2	Weeks 3-4				
Exercise bouts/week	3	4				
Endurance Training	Time: 40-50min	Time: 60 min				
	Intensity: 65-75% HRmax Intensity: 85% HRmax					
Resistance Training	Time: 40-50 min	Time: 60 min				
	Intensity: 65-75% 1rm	Intensity: 75-85% 1rm				
	Protocol: 3x10-12reps	Protocol: 3x8-12reps				
	Increase intensity by 5-10% of 1RM when needed					

Endurance exercise combination group: Only the TRE + EN combination group will partake in the endurance exercise training. Participants will be given two supervised endurance exercise options due to COVID-19, one in-person and one remote. Option 1 (in-person): All training sessions will be conducted at the HNRU. Subjects will participate in a supervised aerobic exercise program 3-4 times per week, 40-60 min/d, for 8 weeks. Exercise will be performed on an elliptical, stationary bike or rowing erg. Participants will be masked, exercise equipment will be placed ≥6ft apart and cleaned between use. During the week 1 sessions, subjects will exercise for 40 minutes at a moderate intensity (65% heart rate max (HRmax)). During the week 2 sessions, subjects will train for 50 minutes at a higher intensity (75% HRmax). For weeks 3-8, subjects will train for 60 minutes at an even higher intensity (85% HRmax). The participants will wear heart rate monitors (Fitbit Alta HR, Boston, MA) during each training session to provide visual feedback of their individualized target heart rate. Fitbit monitors will be distributed to subjects at each training session. Compliance with the training: A research assistant will be present to supervise all the training sessions. Exercise will be carefully documented through attendance at the training sessions. Subjects will be permitted to choose the day and time slot that works best for them. If a subject misses their session, they will be required to make up for it that same week. Subjects will be permitted to miss 4 sessions total during the 8-week intervention.

Strength and Conditioning by [name], MS, ACSM, CSCS. During the baseline period participants will attend two session prior to the intervention for familiarization and testing. The first session will be a familiarization session where the participant will be instructed on how to do the movements correctly and safely. The second session will test the participants' 5rm of deadlift, box squat, overhead press, and bench press. 1RM estimates will be based off of the 5rm (80% of 1rm). Subjects will participate in a supervised resistance training program beginning with 3 times per week progressing to 4 times per week in weeks 3-8. Each session will be 40-60 min in duration and will continue for 8-weeks. During RT session participants will perform a progressive periodized whole-body resistance exercise (exercise program attached to submission). During the first 2 weeks of the RT program, the participants will complete three sets of 10–15 repetitions of 65% of their 1 rep max. For the following 6 weeks, the training volume will be set at three sets of 8–12 repetitions at an intensity of 75-85% of 1 rep max. Each week, weight will progressively increase by 5–10% as needed due to training adaptation. For all exercises, the participants will be instructed to perform each repetition in a slow, controlled manner, with a rest of 1-2 min between sets. The participants will wear heart rate monitors (Fitbit Alta HR, Boston, MA) during each training session to provide visual feedback of their individualized target heart rate. Fitbit monitors will be distributed to subjects at each training session. Compliance with the training: A research assistant will be present to supervise all the training sessions for compliance and correct technique execution. Exercise will be carefully documented through attendance at the training sessions. Subjects will be permitted to choose the day and time slot that works best for them. If a subject misses their session, they will be required to make up for it that same week. Subjects will be permitted to miss 4 sessions total during the 8-week intervention. (see COVID protocols in Subject Safety)

**Control group protocol:** Controls will be instructed to maintain their weight throughout the trial, and not to change eating or physical activity habits. Controls will visit the research center at the same frequency as the treatment groups (for outcome measurements) to control for investigator-interaction bias between groups. Controls will be offered free weight loss diet counseling (4 sessions) at the conclusion of the study by [name]., RD.

**Weekly check-in:** Weekly check-in calls will be done with all participants regardless of group at a prespecified time weekly via either zoom or telephone based on the participant preference. This appointment time will remain the same throughout the 10 weeks. During this call the study coordinator will address possible issues with compliance, difficulty with the intervention, and complete the adverse events questionnaire verbally. Time stamped weigh in photos and adherence logs will also be requested at this appointment. Further, dietary counseling to support the participant will be included in each call by a registered dietitian ([name], RD). Diet counseling will not include weight loss counseling, but general lifestyle improvement so as can be also given to the control group for weight maintenance. All counseling will be based off of recommendations from the Academy of Nutrition and Dietetics, The American Heart Association, and Healthy People 2020. Topics will include:

- Increasing fruit and vegetable intake
- Reading food labels
- Water intake
- Lean protein
- Healthy fats
- Whole grains
- A balanced plate Choices for eating out

*Time restricted feeding with physical activity for weight management Version 4, 07/19/21*  **Subject compensation.** No compensation or parking reimbursement is offered for trial completion. Participants will be able to have access to all data received from the study. In addition, controls will receive 4 free diet counseling sessions at the conclusion of the study.

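### By the plan's own 5RM conversion, the upper part of the 75-85% of 1RM band allows at most five repetitions at tested strength, yet 8-12 are prescribed; the arm's intensity is also stated on two unlinked scales

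*Combined protocol and SAP*

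**What the plan says.** The dose of the TRE + RT arm is stated in three places in section 3.0.

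- **Resistance training paragraph (Exercise protocol).** A baseline session tests the "5rm of deadlift, box squat, overhead press, and bench press". The conversion follows: "1RM estimates will be based off of the 5rm (80% of 1rm"). After the first two weeks, the remaining six weeks use "three sets of 8–12 repetitions at an intensity of 75-85% of 1 rep max". Progression reads "Each week, weight will progressively increase by 5–10% as needed due to training adaptation". The session content is a "progressive periodized whole-body resistance exercise (exercise program attached to submission"); that attachment is not part of the public document.
- **Exercise protocol table.** The later column gives "Intensity: 75-85% 1rm" with "Protocol: 3x8-12reps", and adds "Increase intensity by 5-10% of 1RM when needed". This column is headed weeks 3-4, so the extension to weeks 3-8 rests on the paragraph.
- **Diet and exercise interventions table.** The same arm's intensity is a single value, 85% RPE.

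No repeat 5RM or 1RM test is described, and no place says whether the band refers to the baseline 1RM or to an updated one.

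**The concern.** A 5RM is the heaviest load a person can lift five times. Once the plan fixes the 5RM at 80% of 1RM, every load from 80% of 1RM upward is at or above a load that has just been measured as a five-repetition limit. Asking for eight or more repetitions there contradicts the measurement the load was derived from, unless the participant has since become stronger.

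Load and repetitions are what define this arm. Where they cannot both be met, staff have to give way on one of them, and the text does not say which. Two supervisors, or two participants with the same test result, could then receive different training under the same protocol. A second intensity scale with no link to the first adds to this, because a session could be judged on target by one scale and off target by the other.

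**Working it through.** **Inputs, all from section 3.0**

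- Conversion: 5RM = 0.80 × 1RM (resistance training paragraph).
- Load band: 75-85% of 1RM (paragraph and Exercise protocol table).
- Repetitions: 8-12 per set, three sets (same two places).
- Progression: 5-10% (same two places, with the base worded differently).

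The 80% figure comes from a cited source and is taken as given. No curve relating repetitions to load is used.

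**Step 1. Express the band in units of the tested 5RM.**

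Estimated 1RM = 5RM / 0.80 = 1.25 × 5RM. A load of p × 1RM is therefore p / 0.80 times the tested 5RM.

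| Load, % of estimated 1RM | Multiple of tested 5RM | Repetitions possible at tested strength |
|---|---|---|
| 75 | 0.75 / 0.80 = 0.9375 | at least 5; upper limit not derivable |
| 80 | 0.80 / 0.80 = 1.0000 | 5 |
| 85 | 0.85 / 0.80 = 1.0625 | at most 5 |

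The minimum prescribed is 8. Pairing the lowest repetition count with the highest load does not help, since 8 is already above 5. The conflict covers loads from 80% to 85%, which is (85 − 80) / (85 − 75) = 0.50 of the band in percentage points.

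**Step 2. Does this depend on the conversion being accurate?**

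No. The plan computes 1RM from the 5RM, so 80% of the computed value returns the measured 5RM load whatever the true 1RM is. A different factor would change the result only if the plan adopted it. As an illustration with assumed values, a factor of 0.825 would leave a quarter of the band at or above the 5RM load, (85 − 82.5) / 10 = 0.25, and a factor of 0.85 only the top edge.

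**Step 3. Two readings of the reference 1RM.**

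- *Baseline 1RM.* At 80% the participant must come to lift the baseline 5RM load at least 8 times; at 85%, a load 6.25% above it at least 8 times. For these loads to become 75% of the participant's current 1RM, the 1RM would have to rise by 0.80 / 0.75 − 1 = 6.7% and 0.85 / 0.75 − 1 = 13.3% respectively. The documents do not show whether 8 repetitions are possible even at 75%, so these gains are a scale for the question and not a threshold.
- *Updated 1RM by the same conversion.* 80% of the updated value is the updated 5RM, so at most five repetitions are again possible. Strength gain does not remove the conflict.

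**Step 4. Base of the 5-10% increase.**

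Starting from 75%, one step taken as percentage points of 1RM gives 75 + 5 = 80% to 75 + 10 = 85%, wholly inside the conflicting part. One step taken as a percentage of the current load gives 75 × 1.05 = 78.75% to 75 × 1.10 = 82.5%. The table names 1RM as the base; the paragraph names none.

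**Step 5. Intensity scale.**

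The interventions table uses perceived exertion and one value. The other two places use percentage of 1RM and a range. No conversion is given, so the statements cannot be checked against each other.

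**The case against.** The strongest reply is that tested strength is not the condition the band is written for. The 5RM is measured once, before training. The band begins after two weeks of supervised training in people recruited for low activity, and both progression statements make increases conditional on need. The only 1RM in the documents is the baseline estimate. The natural picture is then a climb through the band as repetitions become achievable. The endurance arm supports this: its table gives a range for weeks 1-2, and its text resolves the range into a lower value in week 1 and the upper value in week 2.

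Much of this stands. The upper part of the band may become reachable, so the plan is not shown to be unworkable. What remains is that this reading has to be supplied by the reader. No place says the band is entered at its lower end, ties it to the baseline value, or varies the repetitions within it. Under the updated reading the conflict is not relieved at all.

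The attached exercise program may settle loads and progression. It could not be seen, and the conversion is stated only for the four tested lifts. Even so, an attachment would not remove the conflict between statements in the protocol itself.

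A reader might also infer that load and repetitions will go unrecorded, because the paragraph names attendance as the documentation. That is not established: every session is supervised, adherence logs are requested at the weekly check-in, and the unseen attachment may cover recording.

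**Conclusion.** The point holds as an internal inconsistency of minor severity. Loads of 80-85% of estimated 1RM equal 1.00-1.06 times the tested 5RM and allow at most five repetitions at tested strength, against a prescribed minimum of eight. Whether training resolves this depends on which 1RM the band refers to, and the text does not say. The mismatch between RPE and percentage of 1RM is a separate inconsistency in the same arm. The result rests on the plan's own conversion and the definition of a 5RM.

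Three stronger inferences are not supported:

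- *The whole band is infeasible.* Loads from 75% to below 80% are lighter than the 5RM, and the documents do not say how many repetitions they allow.
- *Half the sessions, or a given share of repetitions, cannot be delivered.* The 50% in the working is a share of percentage points. The plan does not state how many sessions use 80% or more, or how strength changes.
- *An outcome or estimate is affected.* Strength is not among the scheduled measurements in the Study activities table, and no sample size, estimate or analysis uses these figures. The consequence is confined to how consistently the TRE + RT intervention (n = 5 in section 3.0) is delivered and described.

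**What to change.** The investigators should reconcile the resistance training paragraph, the Exercise protocol table and the Diet and exercise interventions table, so that the 5RM-to-1RM conversion, load band, repetition range and intensity scale agree. They should state:

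- whether the band refers to the baseline 1RM or an updated one and, if updated, how;
- what the 5-10% increase is a percentage of;
- whether intensity is set by percentage of 1RM or by RPE and, if both are kept, how they relate.

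The attached exercise program should be checked against the reconciled text. Which load, repetition range or scale applies is for the investigators to decide, and none is proposed here.

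The cost is protocol wording. The 5RM test and session supervision are already planned, and the analysis is untouched. Only a decision by the investigators to update 1RM by retesting would add a procedure, and this point does not ask for one.

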#### Summary of intervention groups and key outcome measures

# Study activities

Study activities		Base	eline	Intervention (8 weeks)							
	Screen	1	2	3	4	5	6	7	8	9	10
Informed consent	•										
Screening/ Alcohol questionnaire	•										

Body weight	•	•	•	•	٠	٠	•	٠	٠	•	•
Waist circumference		•		•							•
Diet adherence		•		•	•	•	•	•	•	•	•
Fat mass (BIA)		•		•	•	•	•	•	•	•	•
Blood pressure/heart rate		•		•	•	•	•	•	•	•	•
DXA		•									
Blood draw	•	•		•							•
Activity monitor (7-d)		•									•
Food record		•		•							•
Sleep questionnaires		•		•							•
Adverse events survey		•		•	•	•	•	•	٠	٠	•
NeuroTrax Cognition		•		•							•
Quality of life/mood		•		•							•

# 4.0 Data analysis

Data will be analyzed by SPSS software (SPSS v24).

## 5.0 Statistical considerations

All continuous variables will be examined for distributions and the presence of outliers. Variables that are not normally distributed will be transformed and if normality cannot be achieved, will be analyzed using non-parametric tests. Standardized descriptive statistics including measures of means, median, standard deviations, ranges, and standard errors for continuous variables within each group will be calculated to describe the groups at fixed time points. Differences between groups at baseline will be assessed by a one-way ANOVA. A linear mixed model will be used to assess time, diet, and time × diet effects for each outcome. This model will provide unbiased estimates of time and treatment effects under a missing- at-random assumption. Time will not be assumed to be linear in the model. This strategy will allow for estimation of time and diet effects (and their interaction) without imposing a linear time trend. Relations between continuous variables will be assessed by Pearson's or Spearman's correlation coefficients as appropriate. Data will be analyzed using SPSS software (SPSS, Chicago, IL).

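### The claim of unbiased treatment effects rests on missing-at-random alone, which cannot support between-arm effects in a non-randomised trial

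*Combined protocol and SAP*

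**What the plan says.** Section 3.0 sets out the design: "A 10-week non-randomized, controlled, parallel-arm trial, divided into a 2-week baseline and an 8-week intervention will be implemented". On allocation it says "Older subjects with overweight or obesity (n = 20) will be assigned to 1" of four groups: time-restricted eating (TRE), TRE with endurance exercise, TRE with resistance training, and control. It gives no rule, matching or stratification for that assignment. The section 3.0 text has 5 participants per arm; the diet and exercise interventions table in the same section has 50 per arm.

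Section 5.0 gives the analysis: "A linear mixed model will be used to assess time, diet, and time × diet effects for each outcome". It then states: "This model will provide unbiased estimates of time and treatment effects under a missing- at-random assumption". It adds: "This strategy will allow for estimation of time and diet effects (and their interaction) without imposing a linear time trend". No other condition is attached to the claim of unbiasedness. No covariate, propensity method or sensitivity analysis is named, and no sentence says which model term is the treatment effect.

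**The concern.** The sentence attaches one condition, about missing data, to a claim about treatment effects. An unbiased treatment effect also requires that the arms be comparable. Randomisation would provide that by design; here it is absent, and nothing in the plan takes its place.

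The arms make very different demands on participants: several supervised exercise sessions a week, resistance training at a separate gym, or no exercise at all. Motivation or availability could therefore differ between arms and could also influence change in weight or glucose. A reader who takes the sentence at its word would report TRE versus control, or exercise added to TRE, as an unbiased effect of the intervention. The design supports that reading only under an assumption that the plan does not state.

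**Working it through.** The documents contain no power, alpha or bias figure to reproduce. The check has three steps.

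**1. What missing-at-random covers.** Suppose every outcome is observed. Missing-at-random is then satisfied trivially. If the claim can still fail in that case, the stated condition is not sufficient.

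**2. What each model term estimates when there is no treatment effect.** Take arms A and C, with baseline as a level of time.

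- Time-by-group contrast at week 10 = (mean change in A) − (mean change in C). If A lies *d* above C at every visit, this is *d* − *d* = 0. If the arms would have changed by different amounts without treatment, it equals that difference.
- Group main effect = average over visits of (A − C). A stable gap *d* enters in full, as *d*.
- The main effect also dilutes a real effect. If an effect grows linearly from 0 at week 1 to 1.0 at week 10 over nine visits (week 1 and weeks 3 to 10), the main effect is (0 + 1/8 + 2/8 + … + 8/8)/9 = 4.5/9 = 0.5, while the week-10 interaction contrast is 1.0.

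The interaction is therefore the better definition of the treatment effect, but it needs equal change in the absence of treatment. Missing-at-random does not supply that.

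**3. How large the error could be.** Inputs from the documents: 5 per arm (section 3.0 text) or 50 per arm (section 3.0 interventions table). Assumed inputs: complete data, no true effect, SD of change 1 within each arm, an unmeasured trait with correlation *r* with change and a between-arm difference of δ SD, and a two-sided t-test of change between two arms at 0.05.

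- Bias = *r* × δ, in SDs of change. Sample size does not enter.
- Standard error = √(2/n): √(2/5) = 0.632; √(2/50) = 0.200.
- Noncentrality = bias / standard error, with 2n − 2 degrees of freedom.

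| *r* | δ | Bias | n per arm | Noncentrality | False positives |
|---|---|---|---|---|---|
| 0.5 | 1 | 0.50 | 5 | 0.50/0.632 = 0.79 | about 11% |
| 0.5 | 1 | 0.50 | 50 | 0.50/0.200 = 2.50 | about 70% |
| 0.1 | 0.5 | 0.05 | 5 | 0.05/0.632 = 0.08 | about 5% |
| 0.1 | 0.5 | 0.05 | 50 | 0.05/0.200 = 0.25 | about 6% |

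A simulation of 20,000 trials for the *r* = 0.5, δ = 1 case gave biases of 0.497 and 0.500, with rejection rates of 10.6% (n = 5) and 69.7% (n = 50). With δ = 0 the bias was about zero and rejection about 5% at both sizes. No data were missing in any of these cases.

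**The case against.** The best defence is that the sentence is conditional and, in context, describes how a mixed model handles missing data; section 3.0 openly calls the trial non-randomised. The natural reading of the model is also that time-by-diet is the effect of interest, and that term removes a stable baseline gap. Both points have force. The fault is then incomplete wording rather than a wrong model. But the wording names treatment effects, and the interaction still needs the equal-change assumption, so the claim fails on the charitable reading too.

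A second defence is that false positives barely rise in a small pilot. At 5 per arm that is fair, but the bias does not shrink with more participants, and at the table's 50 per arm false positives would rise sharply in the larger example.

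Four stronger inferences are tempting, and the documents do not support them:

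- *The main effect will be reported as the treatment effect, with grossly inflated error.* The plan does not say so. High rejection rates computed for that term do not measure the harm here.
- *A non-significant baseline test will be taken as proof of comparability.* Section 5.0 says only "Differences between groups at baseline will be assessed by a one-way ANOVA".
- *Diet is a two-level factor that mixes exercise into the TRE effect.* Three arms do share one diet, but section 5.0 speaks of groups and of treatment effects, which suggests a loose label for the four arms.
- *Participants chose their arm, so the results are biased.* The assignment method is not given. A baseline gap that regresses towards the mean would not show selection either, since chance imbalance in a randomised trial behaves the same way.

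**Conclusion.** The concern holds as a fault in the stated claim. With non-random assignment, no stated rule and no planned adjustment, the model does not guarantee unbiased between-arm effects, whether or not outcomes are missing. Whether bias will occur, and how much, cannot be derived from the documents. The 0.5 SD example rests on an assumed correlation and imbalance, and weaker values give as little as 0.05 SD. The direction is also unknown.

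The conclusion is the same at 5 or 50 per arm, but the effect on false positives is not, so the two arm sizes must be reconciled before anyone judges how much this matters in practice. The point should be corrected before analysis; it does not call the choice of a mixed model into question.

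**What to change.** 1. Replace the sentence in section 5.0 with: *Under a missing-at-random assumption, and if the model is correctly specified, missing outcome data do not bias the estimates. Because participants are not randomised, differences between arms may be confounded.*
2. State that the treatment effect is the time-by-group interaction, with four groups and baseline as a level of time: the between-arm difference in change from baseline to week 10, not the group main effect.
3. State that a causal reading assumes the arms would have changed equally without the intervention.
4. Name in advance the arm pairs to be compared and the pre-intervention visit that serves as baseline. Both choices are the sponsor's. The second needs care because the study activities table shows several outcomes in weeks 1 and 3, and body weight in weeks 1 and 2 as well.
5. Reconcile the arm sizes in section 3.0.
6. Optionally, report a model adjusted for the baseline value of the same outcome as a sensitivity analysis, noting that it does not remove confounding. If the two models disagree, report both.

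The cost is SAP wording and, if chosen, one further model; no extra data or visits are needed. The downside is weaker stated conclusions and slightly more analysis.

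### The planned Pearson or Spearman correlations make no allowance for arm; run on post-baseline values or changes pooled across arms, they can pick up the treatment contrast as an association

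*Combined protocol and SAP*

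**What the plan says.** The correlation plan is one sentence in Section 5.0: "Relations between continuous variables will be assessed by Pearson's or Spearman's correlation coefficients as appropriate". Coming after the text on normality and non-parametric tests, the closing words read as a choice between the two coefficients by distribution. Nothing in Sections 4.0 or 5.0 says which variables are meant, at which visit, as raw values or changes, or over which participants.

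Arm appears in the same section in three other places. Baseline group differences get a one-way ANOVA. The treatment comparison is "A linear mixed model will be used to assess time, diet, and time × diet effects for each outcome", so group is modelled one outcome at a time. The only within-group wording concerns descriptive statistics: "standard errors for continuous variables within each group will be calculated to describe the groups at fixed time points".

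Section 3.0 describes "A 10-week non-randomized, controlled, parallel-arm trial, divided into a 2-week baseline and an 8-week intervention will be implemented". It gives the total as "Older subjects with overweight or obesity (n = 20) will be assigned to 1" of four groups, three of them on TRE and the fourth "control (n = 5), ad libitum food intake daily with no meal timing restrictions". The Diet and exercise interventions table prints 50 per group instead of 5. Under the control group protocol, "Controls will be instructed to maintain their weight throughout the trial, and not to change eating or physical activity habits".

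**The concern.** The design sets out to create a contrast: three arms change their eating pattern, two of these also train, and the control arm is asked to stay as it is. When two variables respond in the same arms, the arm means alone line up and produce a correlation in the pooled sample. A plain coefficient cannot tell this from a link between the variables among people who received the same intervention. Because allocation is not randomized, arm differences at baseline could act in the same way.

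This sentence is the only analysis in the plan of how variables relate to one another. What is at stake is a report that, say, change in weight goes with change in glucose, when the data show only that both moved under treatment.

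**Working it through.** The plan states no correlation, alpha, SD or effect size, so there is no figure of its own to reproduce. The check is whether the mechanism works in this design, and how strongly.

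**Inputs from the documents (Section 3.0).** Four arms of 5, N = 20; three of the four arms on TRE, so the TRE share is p = 0.75. The alternative arm size in the interventions table is 50, N = 200.

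**Assumptions.** Two-sided 0.05; zero correlation within every arm; both variables shifted by d within-arm SDs in all three TRE arms; one pair of values per participant.

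**Induced correlation.** The arm means contribute p(1 − p)d² = 0.75 × 0.25 × d² = 0.1875d² to the covariance, and the same amount to each variance on top of a within-arm variance of 1. Hence r = 0.1875d² / (1 + 0.1875d²):

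- d = 0.5: 0.0469 / 1.0469 = 0.045
- d = 1: 0.1875 / 1.1875 = 0.158
- d = 1.5: 0.4219 / 1.4219 = 0.297
- d = 2: 0.75 / 1.75 = 0.429

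If the two variables move in opposite directions, r has the same size with a negative sign.

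**False-positive rates by simulation** (20,000 replicates at 5 per arm, 4,000 at 50 per arm). The arm-adjusted column uses residuals from arm means on N − 2 − 3 df.

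| Per arm | d | Pearson | Spearman | Arm-adjusted |
|---|---|---|---|---|
| 5 | 0 | 4.9% | 4.8% | 5.0% |
| 5 | 0.5 | 5.2% | 5.3% | 4.9% |
| 5 | 1 | 10.3% | 9.6% | 4.8% |
| 5 | 1.5 | 26.2% | 22.6% | 4.9% |
| 5 | 2 | 52.8% | 42.2% | 5.1% |
| 50 | 0.5 | 9.5% | 9.2% | 4.5% |
| 50 | 1 | 62.9% | 59.3% | 5.3% |
| 50 | 1.5 | 99.5% | 99.1% | 4.8% |

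Spearman lowers the rate somewhat but does not remove the problem. As a cross-check at N = 200 and d = 1, Fisher's z for r = 0.158 is 0.159, and 0.159 × √197 = 2.24, which gives a rejection rate of about 0.61.

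**Where the mechanism fails** (5 per arm, Pearson):

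- Only one variable shifts, d = 1: mean r 0.003, rate 5.3%.
- Shifts of (1, 1, 0, 0) in one variable and (1, 0, 1, 0) in the other: the arm-mean covariance is 0.25 − 0.5 × 0.5 = 0; simulated mean r 0.003, rate 4.4%.

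Aligned but unequal shifts do inflate: (1, 1.5, 1.5, 0) in both variables gives mean r 0.282 and a rate of 22.3%.

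**Critical |r| = t / √(t² + df).** Pooled N = 20, 18 df: 0.444. Arm-adjusted N = 20, 15 df: 0.482. One arm of 5, 3 df: 0.878.

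**The case against.** The strongest reply is that the sentence does not describe the criticised analysis. It mentions neither outcomes, changes, p-values nor pooling, and correlations among baseline values would fit it equally well and carry no treatment shift. That stands, so the point is conditional on post-baseline values or changes being pooled across arms. The plan nevertheless permits that analysis and offers no adjustment for it.

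A reader might go further and infer that pooling all 20 is the only workable version, since one arm of 5 needs |r| above 0.878. The documents do not support this. Correlating within the 15 TRE participants is possible (critical |r| about 0.51) and induces nothing if those three arms share the same shift. At the 50 per arm in the interventions table, a single-arm correlation is practical (critical |r| about 0.28). A reader might also infer that visits will be stacked as independent rows. Section 5.0 does not propose that; it only fails to exclude it.

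A second reply is that removing arm discards signal: if weight loss itself lowers glucose, the between-arm covariance is part of that relation. This has some force, because the adjusted coefficient describes association within arms only. But a pooled coefficient cannot separate such a link from a treatment that moves both variables independently, so it is the weaker basis for a statement about how the variables relate.

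Third, nothing in the documents shows that cognition, mood or glucose would shift by 1 to 2 SD in eight weeks. That also stands: the larger rates are scenarios.

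**Conclusion.** The point holds in conditional form. As stated, the method makes no allowance for arm, and on post-baseline values or changes pooled across arms it can report the TRE-versus-control contrast as an association. At 5 per arm the effect is negligible for shared shifts up to about 0.5 SD and becomes material from about 1 SD (10%, rising to 26% and 53% at 1.5 and 2 SD). At 50 per arm it is already about 60% at 1 SD. These rates rest on the assumed d, alpha, zero within-arm correlation and aligned shifts.

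It would be too strong to say that unrelated variables will correlate under this plan, or that its error rate is 26% or 53%: without aligned shifts there is no inflation. Nor does the point reach the treatment comparison, since the time, diet and time × diet estimates come from the mixed model. This is a secondary analysis that should be corrected because a better method is available at little cost.

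**What to change.** Replace the correlation sentence in Section 5.0 with text to this effect:

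*The variables and time points to be correlated are listed in advance. Any correlation of post-baseline values or changes uses one pair of values per participant (for example, week 10 minus week 1) and is adjusted for the four-level arm, by partial Pearson correlation or by Spearman correlation of arm-centred values. Repeated visits are not treated as independent rows. Baseline-only correlations are labelled as such and preferably also adjusted for arm, because allocation is not randomized.*

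Baseline correlations should remain allowed. A rule that forced every correlation onto changes would bar them, and would exclude DXA, which the Study activities table shows only at week 1.

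The cost is SAP wording and three degrees of freedom: with complete pairs at N = 20, 18 df become 15 and the critical |r| rises from 0.444 to 0.482. No new data are needed for variables already measured at weeks 1 and 10. Reports should say that the adjusted coefficient describes association within arms.

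Separately, the arm size must be reconciled between the Section 3.0 text (5) and the interventions table (50), because the size of this problem depends strongly on it.
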